11.10.9 Excluded Concomitant Medications and Procedures

Because DS-3201b is primarily metabolized by the liver, the following medications and procedures are prohibited during the study:

- Administration of other antineoplastic agents during the study is prohibited.
- Strong CYP3A4/5 inhibitors / inducers, and/or P-gp inhibitors, grapefruit juice, and St. John's wort are prohibited except when prophylactic administration is required for the treatment of symptoms such as infection.
- If strong or moderate CYP3A inducers are medically essential to use as supportive care, concomitant use of moderate and strong CYP3A inducers is permissible after the first dose of DS-3201b. In this case, dose interruption of DS-3201b tosylate is not needed. Avoid the concomitant use as much as possible because drugs having

moderate or strong CYP3A-inducing properties may decrease the plasma concentration of DS-3201b.

- Consumption of herbs/foods that may have an influence on PK of DS-3201b such as St. John's wort, star fruit, Seville orange or Seville orange-containing foods and beverages, grapefruit or grapefruit-containing food or beverages from 14 days prior to the start of the study and throughout the entire study.

CYP3A Inducers and Inhibitors can be found at the following site:
<http://medicine.iupui.edu/clinpharm/ddis/table.aspx>

Prohibited Concomitant Medications Due to Known Risk of QT Prolongation

The following drugs are known to prolong QT and to be clearly associated with Torsades de Pointes (TdP). Patients are encouraged to discontinue or refrain from starting any of the following medications while on study with the exception of ondansetron, which is part of the standard pre-medications for irinotecan infusion. For all of the medications listed below,

patients are still allowed to continue or start these medications if truly medically necessary or as part of routine chemotherapy regimen.

- amiodarone
- anagrelide
- azithromycin
- chloroquine
- chlorpromazine
- cilostazol
- ciprofloxacin
- citalopram
- clarithromycin
- disopyramide
- dofetilide
- donepezil
- dronedarone
- droperidol
- erythromycin
- escitalopram
- flecainide
- fluconazole
- haloperidol
- ibutilide
- levofloxacin
- methadone
- moxifloxacin
- ondansetron*
- pentamidine
- pimozide
- procainamide
- propofol
- quinidine
- sevoflurane
- sotalol
- thioridazine

*Excluded from the list of prohibited medicines due to its inclusion as a part of the standard pre-medications for irinotecan infusion

This full list of medications can be found at the following site:
<https://crediblemeds.org/new-drug-list/>

11.11 Precautions and Restrictions

Pregnancy

It is not known what effects DS-3201b has on human pregnancy or development of the embryo or fetus. Therefore, female patients participating in this study should avoid becoming pregnant, and male patients should avoid impregnating a female partner. Nonsterilized female patients

of reproductive age group and male patients should use highly effective methods of contraception through defined periods during and after study treatment as specified below.

Female patients must meet 1 of the following:

- Postmenopausal for at least 1 year before the screening visit, or
- Surgically sterile, or
- If she is of childbearing potential, agree to practice 1 highly effective method and 1 additional effective (barrier) method of contraception, at the same time, from the time of signing the informed consent through 6 months after the last dose of study drug, or
- Agree to practice true abstinence, when this is in line with the preferred and usual lifestyle of the subject. (Periodic abstinence [e.g., calendar, ovulation, symptothermal, postovulation methods] withdrawal, spermicides only, and lactational amenorrhea are not acceptable methods of contraception. Female and male condoms should not be used together.)

Female patients must agree to not donate eggs (ova) during the course of this study or 4 months after receiving their last dose of study drug(s).

Male patients, even if surgically sterilized (i.e., status post vasectomy), must agree to 1 of the following:

- Practice highly effective barrier contraception during the entire study treatment period and through 6 months after the last dose of study drug, or
- Practice true abstinence, when this is in line with the preferred and usual lifestyle of the subject. (Periodic abstinence [e.g., calendar, ovulation, symptothermal, postovulation methods for the female partner] withdrawal, spermicides only, and lactational amenorrhea are not acceptable methods of contraception. Female and male condoms should not be used together.)
- Male patients must agree to not donate sperm during the course of this study or 6 months after receiving their last dose of study drug(s).

12.0 CRITERIA FOR THERAPEUTIC RESPONSE/OUTCOME ASSESSMENT

Determining the Safety, Tolerability, MTD and RP2D of DS-3201b in Combination with Irinotecan

The Common Terminology Criteria for Adverse Events (CTCAE) 5.0 will be used to determine all adverse events and dose-limiting toxicities.

Determining the Objective Response Rate (ORR) to Treatment with DS-3201b at the RP2D in Combination with Irinotecan

The Response Evaluation Criteria in Solid Tumors Group (RECIST v1.1) criteria will be used to evaluate the response to treatment.²⁹

Target Lesions

Change in disease will be assessed by repeat chest/abdomen/pelvis CTs at baseline and at every other cycle thereafter.

Complete Response (CR): Complete absence of all signs of disease without any new lesions or disease-related symptoms.

Partial Response (PR): A reduction of $\geq 30\%$ as compared to the baseline measurement.

Stable disease (SD): Neither sufficient shrinkage to qualify for PR nor sufficient increase to qualify for PD taking as references the smallest sum the longest diameter (LD) since the treatment started.

Progressive Disease (PD): An increase of $\geq 20\%$ over the nadir measurement is defined as progressive disease.

Non-Target Lesions

All other lesions (or sites of disease) not included in the "target lesions," including small lesions (longest diameter < 20 mm with conventional techniques or < 10 mm with spiral CT scan) and truly non-measurable lesions, should be identified as non-target lesions and recorded at baseline. Measurements are not required, and these lesions should be followed as defined below.

Lesions that are considered non-measurable include bone lesions, leptomeningeal disease, ascites, pleural/pericardial effusion, abdominal masses that are not confirmed and followed by imaging techniques, and cystic lesions.

Complete response: Disappearance of all non-target lesions.

Non-complete response/Non-progression: Persistence of one or more non-target lesions.

Progression: Appearance of one or more new lesions. Unequivocal progression of existing non-target lesions.

Evaluation of Best Overall Response

The best overall response is the best response recorded from the start of the treatment on Cycle 1 Day 1 until disease progression/recurrence (taking as reference for progressive disease the smallest measurements recorded since the treatment started). If patients remain on treatment with partial response or stable disease past 6 months from the date of Cycle 1 Day 1, the first 6 months of treatment will be used to evaluate the primary endpoint of best overall response. In general, the patient's best response assignment will depend on the achievement of both measurement and confirmation criteria.

Target Lesions	Non-target Lesions	New Lesions	Overall Response
CR	CR	No	CR
CR	Non-CR/Non-PD	No	PR
PR	Non-PD	No	PR
SD	Non-PD	No	SD
PD	Any	Yes or No	PD
Any	PD	Yes or No	PD
Any	Any	Yes	PD

Patients with a global deterioration of health status requiring discontinuation of treatment without objective evidence of disease progression at that time should be reported as "symptomatic deterioration." Every effort should be made to document the objective progression even after discontinuation of treatment.

Conditions that may define early death include patients that have died without documentation of disease progression and before it was time to conduct the first tumor reassessment. Inevaluable patients include those who have received protocol treatment but did not have any follow-up assessment completed before initiation of alternative treatment.

In some circumstances, it may be difficult to distinguish residual disease from normal tissue. When the evaluation of complete response depends upon this determination, it is recommended that the residual lesion be investigated (fine needle aspirate/biopsy) before confirming the complete response status.

Guidelines for Evaluation of Measurable Disease

All patients in this study will be getting a baseline CT scan to include the target lesion (Table 3).

Confirmation Measurement/Duration of Response or Duration of Stable Disease

In patients who are confirmed to have CR/PR, the duration of overall response is measured from the time measurement criteria are met for CR/PR (whichever is first recorded) until the first date that recurrent or progressive disease is objectively documented (taking as reference for progressive disease the smallest measurements recorded since the treatment started).

In patients who are confirmed to have stable disease, the duration of stable disease is measured from the start of the treatment until the criteria for progression are met, taking as reference the smallest measurements recorded since the treatment started.

Determining the Progression-Free Survival (PFS) and Overall Survival (OS)

Kaplan-Meier analyses will be used to estimate the PFS and OS.

Correlative Studies

Descriptive analyses as described in Section 10.0 will be used to report all correlative testing results obtained from this study.

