³ Urinalysis will include assessments of turbidity and color, pH, specific gravity, protein, ketones, bilirubin, occult blood, nitrite, glucose, and leukocyte esterase. Urine microscopic analysis will include erythrocytes, leukocytes, bacteria, casts, and crystals.

⁴ CT scans and brain MRIs will be obtained at the completion of every 2 cycles (approximately every six weeks).

⁵ CTCs for PDX engrafting will only be collected from samples from patient's treatment at MSKCC main campus. Due to feasibility barriers with transporting samples, no patient samples from MSKCC Regional Care Centers or from JHU will be collected for this purpose. Each sample will include two 10 cc EDTA tubes to be transported on ice.

⁶ CTCs for analysis by EPIC Sciences will be collected from all MSKCC sites and all JHU sites. Each sample will include one 10 cc Streck tube to be transported at room temperature.

⁷ CTCs for banking at MSKCC will be collected from all MSKCC sites and all JHU sites. Each sample will include one 10 cc Streck tube to be transported at room temperature.

⁸ Any fresh tissue biopsy will be performed ONLY if deemed medically safe by the institutional PI. There will be a window of +/- 4 days for the biopsy. The pre-treatment tissue sample can be archival if there is adequate tissue.

⁹ Post-progression tissue biopsy is OPTIONAL.

¹⁰ PK draws: There is a \pm 15-minute window for PK blood draws. PK assessments will be obtained in both Phase I and Phase II. Please see Table 4 for the complete PK schedule. Each PK blood draw will include 5 cc of blood collection.

Table 4.0 Pharmacokinetics (PK) Schedule for DS-3201b (Phase I and Phase II)

Cycle and Day	Time point						
7 days prior to C1D1	0.5-hour post-dose	1-hour post-dose	2-hour post-dose	4-hour post-dose	6-hour post-dose	8-hour post-dose	
Cycle 1 Day 1	Pre-dose	0.5-hour post-dose	1-hour post-dose	2-hour post-dose	4-hour post-dose	6-hour post-dose	8-hour post-dose
Cycle 1 Day 8	Pre-dose						
Cycle 1 Day 15	Pre-dose	0.5-hour post-dose	1-hour post-dose	2-hour post-dose	4-hour post-dose	6-hour post-dose	8-hour post-dose
Cycle 2 Day 1	Pre-dose						

Correlative Studies:

Studies Using Tumor Tissue:

We will obtain mandatory on-treatment core biopsies at Cycle 3 Day 1 +/- 4 days. The Cycle 3 Day 1 biopsy may be canceled if deemed medically unsafe (e.g., prior biopsy resulting in pneumothorax or other complication, bleeding diathesis, etc.) by the PI. The end of trial (EOT) biopsy will be optional.

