Adverse events will be graded according to the CTCAE version 5.0, with patients being assessed weekly while on the treatment. Data on pharmacokinetics (PK) of DS-3201b after DS-3201b administered alone or in combination with irinotecan will be collected 7 Days prior to C1D1, on C1D1, on C1D8, on C1D15 and on C2D15 for each patient in the phase I component of this study. Standard plasma PK parameters for each of the above timepoints will include the maximum plasma concentration (Cmax), minimum plasma concentration (Cmin), and time to maximum plasma concentration (Tmax). The area under the plasma concentration versus time curve (AUC) for DS-3201b will be estimated using non-compartmental analysis and/or a population PK approach.

Phase II:

The second phase of this study will be an open-label, single arm, phase II study of DS-3201b at the established RP2D in combination with fixed dose irinotecan. The primary objective of this study is to assess efficacy, ORR defined as CR+PR measured by RECIST v1.1.

Historical control:

We base the sample size calculation on the estimated response rate of 16% as a benchmark, which we derive from the reported study from Le Chevalier et al.³⁰ A two-stage Simon's minimax design will be employed to test the null hypothesis that the true ORR is 16% versus the alternative hypothesis that the true ORR is at least 35% with a type I error of 0.05 and a power of 0.8. In the first stage, 16 patients will be accrued. The first 6 patients out of this initial 16-patient cohort will be the 6 patients treated at MTD in Phase I.

Efficacy will be measured by RECIST v1.1 assessed response to therapy. If there are 2 or fewer responses in these 16 patients, the study will be stopped early for futility. The probability of stopping the study early for futility is 52% per the two-stage Simon's minimax design. If at least 3 patients show response in this first stage, we will request permission from the sponsor to enroll an additional 15 patients in the second stage. At the end of the study, if ≥ 9 patients out of total of 31 enrolled patients show a partial response or a complete response, then further investigation of DS-3201b in combination with irinotecan will be considered worthwhile.

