The ORR is defined as the proportion of patients with CR, or PR at any reassessment after start based on RECIST v1.1 criterion. The time frame for evaluating the primary endpoint of ORR for this portion of the study will be 6 months from the date of Cycle 1 Day 1 for each patient. The ORR and corresponding exact 95% CI will be reported. Progression-free survival will be measured from the start of treatment until the documentation of disease progression or death due to any cause, whichever occurs first, and censored on the date of last tumor assessment. In addition, we will document absence of tumor progression for patients who are still alive prior to data cutoff, dropout, or the initiation of alternate anticancer treatment. Overall survival will be determined as the time from the start of DS-3201b treatment to death, and censored on the last follow-up date. PFS and OS will be evaluated using the Kaplan-Meier method. The duration of response (for those with CR or PR) and durable of stable disease while on treatment (for those with SD) will also be evaluated using the Kaplan-Meier method.

All recorded toxicity data and adverse events of DS-3201b will be listed and tabulated by system organ class, preferred term and treatment. Any significant vital signs and clinical laboratory test results will be listed and summarized. Any significant physical examination findings and clinical laboratory results will be listed.

As secondary objectives, we will explore downstream mechanistic biomarkers of DS-3201b including SLFN11 expression and H3k27me3 signature by descriptive and graphical summaries of assays performed on tissue samples obtained during the study. The Wilcoxon rank sum test will be used to assess SLFN11 expression by immunohistochemistry as a potential predictive biomarker of response to DS-3201b and to correlate with trimethylation of H3K27 as measured by immunohistochemistry in pretreatment, on-treatment and post-treatment tissue samples as well as in circulating tumor cells (CTCs). In addition, next-generation sequencing (NGS) will also be performed on pre-treatment, on-treatment and post-treatment tissue samples obtained from the study. This data will be analyzed using descriptive

and graphic summaries of the assays performed, including use of gene expression heat maps and advanced computational biostatistics with collaborators in the [name] laboratory.

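### The printed target-lesion progression rule is a purely relative 20% over nadir, with no absolute minimum and no statement whether it or RECIST v1.1 prevails

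*Combined protocol and SAP*

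**What the plan says.** Section 12.0 of the combined protocol and SAP introduces response assessment by naming RECIST v1.1, whose "criteria will be used to evaluate the response to treatment". It then writes out its own definitions. For target lesions, progressive disease is an increase of 20% or more "over the nadir measurement is defined as progressive disease". No minimum increase in millimetres appears anywhere in the documents, and no repeat scan is required before progression is recorded.

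The reference is the running minimum: "taking as reference for progressive disease the smallest measurements recorded since the treatment started". The same section places lesions "< 10 mm with spiral CT scan" among the small, non-target ones, so a single lesion of 10 mm can be a target lesion.

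Progression under this definition feeds several endpoints:

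- Duration of response runs "until the first date that recurrent or progressive disease is objectively documented" (Section 12.0).
- Duration of stable disease ends when the criteria for progression are met (Section 12.0).
- PFS runs "until the documentation of disease progression or death due to any cause" (Section 14.0).
- The period over which best overall response is taken closes at progression (Section 12.0).

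Section 14.0 again names the external standard: "Efficacy will be measured by RECIST v1.1 assessed response to therapy". Neither section says whether the printed definition or the cited guideline governs if they differ.

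**The concern.** A relative threshold shrinks with the reference. The reference here is the smallest of several measurements, each with error, so it tends to lie below the true size. The deeper the response, the smaller the nadir and the fewer millimetres it takes to reach 20%. A patient whose sum falls from 40 mm to 12 mm meets the printed rule at 12 x 1.2 = 14.4 mm, a change of 2.4 mm.

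If a change of that size is within reading error, some progressions will be artefacts. They will fall most often on patients with small residual disease, and they shorten duration of response, duration of stable disease and PFS. Phase II runs at two centres and the documents mention no central read. Without an order of precedence, one assessor may apply the printed sentence and another the cited guideline, and score the same scan differently.

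**Working it through.** **The plan's own figures.** The documents give no measurement error and no rate of false progression, so there is nothing of that kind to reproduce. The only related figures are those of the Simon design in Section 14.0. With stage 1 stopping at 2 or fewer responses in 16 and success at 9 or more in 31:

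- P(X ≤ 2 | n = 16, p = 0.16) = 0.516 (stated: 52%)
- exact type I error 0.047 (limit 0.05)
- power at 35% = 0.801 (stated: 0.8)

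The design reproduces, and this point does not change it.

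**Step 1: smallest growth that meets the printed rule (no assumption needed).** Threshold = 0.20 x nadir sum.

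| Nadir sum (mm) | 10 | 15 | 20 | 25 | 30 | 50 |
|---|---|---|---|---|---|---|
| Growth scored as progression (mm) | 2.0 | 3.0 | 4.0 | 5.0 | 6.0 | 10.0 |

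**Step 2: where an absolute floor would matter.** A floor of F mm binds only if 0.20 x nadir < F, that is, if nadir < 5F: below 15 mm for F = 3, 20 mm for F = 4, 25 mm for F = 5. A nadir of 15 mm after exactly a 30% reduction implies a baseline sum of 15/0.70 = 21.4 mm. Deeper responses reach 15 mm from larger baselines.

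**Step 3: chance of false progression at one comparison.** Assume one target lesion of constant true size L, and independent normal errors with SD s on both scans. Progression is scored if m2 ≥ 1.2 x m1, so P = Φ(−0.2L / (s√(1 + 1.2²))) = Φ(−0.2L / 1.562s). With s = 1 mm:

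- L = 10: Φ(−1.28) = 10%
- L = 15: Φ(−1.92) = 2.7%
- L = 20: Φ(−2.56) = 0.5%

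**Step 4: cumulative chance against the running nadir.** Section 10.1 states that "CT scans and brain MRIs will be obtained at the completion of every 2 cycles", about every six weeks. The simulation takes four scans with no true change, which gives three comparisons with the running minimum (at least 200,000 simulated patients per cell). The SD range is an assumption.

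| True size (mm) | Rule | SD 0.5 | SD 1 | SD 1.5 | SD 2 |
|---|---|---|---|---|---|
| 10 | 20% only | 2.7% | 37% | 61% | 72% |
| 15 | 20% only | 0.04% | 13% | 37% | 55% |
| 20 | 20% only | 0% | 3% | 19% | 37% |
| 10, 15 or 20 | 20% and 5 mm | 0% | 0.1% | 5% | 17% |
| 30 | either rule | 0% | 0.03% | 2.8% | 12.5% |
| 50 | either rule | 0% | 0% | 0.01% | 0.4% |

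With four comparisons, roughly the follow-up scans in six months, the 20%-only figures at 10 mm rise to 4/50/74/85% for the four SDs.

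**Step 5: route to ORR.** Section 14.0 counts a CR or PR at any reassessment. A false progression after a recorded response does not remove it, unless the confirmation mentioned in Section 12.0 is applied and the false progression comes first. Before any response, the risk at the first follow-up scan is the one in Step 3, and it applies only to small baseline sums.

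**The case against.** The strongest reply is that the protocol adopts RECIST v1.1 by name in Section 12.0 and again in Section 14.0, and that the printed line is a summary of that standard, not a rival rule. This stands in part. A reader might infer that the investigators chose a relative-only rule and that changes of 2 to 3 mm will be scored as progression. The documents do not show that. They show an incomplete definition beside a named standard, with no order of precedence. The reply does not remove the point, however, because an assessor who applies the printed sentence is following the protocol.

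Three further objections also narrow the point:

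- **Measurement error.** The documents give none. Calling 2 to 3 mm ordinary reading error would be an assumption. At SD 0.5 mm the problem almost disappears.
- **Scope.** A 5 mm floor matters only for nadir sums below 25 mm. With three 10 mm lesions (sum 30 mm), false progression is the same with or without it. No distribution of target sums is given.
- **Consequence.** A reader might infer that the go/no-go decision is biased. PFS and the two durations are secondary single-arm Kaplan-Meier summaries with no test attached, and ORR is exposed only by the narrow route in Step 5.

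The 5 mm figure has no source in the documents and is offered only as a proposal.

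**Conclusion.** The point holds as a defect in the written definition. The printed rule has no absolute minimum, and its relation to the cited standard is not stated. Applied literally, it can score 2.0 mm of growth at a 10 mm nadir, or 3.0 mm at 15 mm, as progression, and so end duration of response, duration of stable disease and PFS early.

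The millimetre thresholds are exact. The false-progression rates rest on an assumed SD of 0.5 to 2 mm, one lesion, normal errors, no true change and three comparisons. Across that range they run from about 3% to 72% at 10 mm and from about 0% to 55% at 15 mm. The share of patients with nadir sums this small cannot be derived from the documents, so no overall bias in median PFS or duration of response can be stated. The correction is worth making because it is cheap and removes an ambiguity between sites. It does not call the Simon design into question.

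**What to change.** In Section 12.0, for scoring best response, duration of response, duration of stable disease and PFS, define target-lesion progression as an increase of at least 20% over the smallest on-study sum **and** a stated absolute minimum increase in that sum. A minimum of 5 mm is proposed here as an assumption; the sponsor should fix the value knowing that a floor of F mm acts only below a nadir of 5F. Add a statement of whether the printed summary or the cited RECIST v1.1 text prevails where they differ, and refer to the same definition in Section 14.0.

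The cost is about two sentences. The downside is that true growth in very small sums may be recorded as progression one scan later. Progression is also a reason to stop study treatment in Section 13.1, so the sponsor should reconcile that section with the completed definition. No treatment rule is proposed here.

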Study enrollment of the 17th patient will be suspended until the determination of the first-stage results, unless the benchmark of 3 patients with radiographic response is achieved by then. All patients will be included in the primary analysis, even if there are major protocol deviations. Patients are considered non-responses (PD) if they are not evaluable (including if CT scan evaluation not available) or died during the study. This study requires accrual of a minimum of 16 patients and up to a maximum of 31 patients if the cohort is expanded to the second stage. The accrual time is estimated to be between 10-24 months at the rate of 3 patients per month and a likely planned 4 months suspension between the first and second stages of this Phase II study.

To protect patients from excessive toxicity, a stopping rule for toxicity will be implemented during Phase II. Since the 6 patients treated at RP2D in Phase I will be included in the Phase II portion of the study, the early stopping rule for toxicity is calculated based on 31-

6=25 newly recruited patients. This toxicity rule will apply for the entire duration of the Phase II portion of the study.

Stopping rule:

Number of recruited patients	5	10	15	20	25
Number of DLT to stop the trial	≥2	≥3	≥3	≥3	≥4

Operating characteristics of the stopping rule:

True DLT rate	0.05	0.09	0.13	0.17	0.21	0.25
Probability of stopping the trial	0.09	0.30	0.54	0.74	0.87	0.94

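### Duration of response and of stable disease end only at progression; read literally, deaths without documented progression are censored and duration of response is biased upward

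*Combined protocol and SAP*

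**What the plan says.** Both durations are secondary objectives of Part II (Section 2.1).

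- **Duration of response, Section 12.0.** It starts when the criteria for complete or partial response are first met and runs "until the first date that recurrent or progressive disease is objectively documented".
- **Duration of stable disease, Section 12.0.** Here "the duration of stable disease is measured from the start of the treatment until the criteria for progression are met".
- **Analysis, Section 14.0.** Duration of response and "durable of stable disease while on treatment (for those with SD) will also be evaluated using the Kaplan-Meier method". No event list or censoring rule follows for either duration.
- **PFS, Section 14.0, same paragraph.** The clock starts when treatment starts and runs "until the documentation of disease progression or death due to any cause, whichever occurs first, and censored on the date of last tumor assessment".

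Death is named in the PFS definition and in neither duration definition. The restriction of stable disease to time on treatment appears in Section 14.0 and not in Section 12.0.

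**The concern.** A Kaplan-Meier analysis needs every patient to end in an event or a censoring. If progression is the only event, a responder who dies with no progression on record can only be censored. The estimator then treats that patient as having the same future risk of progression as those still followed. In recurrent small cell lung cancer, a death soon after the last scan is unlikely to be unrelated to the disease, so the censoring is informative. The resulting curve describes a longer response than patients actually lived through.

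It also sets two endpoints against each other. Duration of stable disease (as Section 12.0 has it) and PFS both start at the start of treatment. The same death would be an event in one and a censored time in the other.

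Such deaths are plausible under this plan. Section 12.0 foresees patients who stop for clinical deterioration without objective progression and records them under a separate label. Table 3.0 marks CT at baseline and from Cycle 3, with footnote 4 tying scans to every two cycles; it marks none at end of treatment. After treatment, Section 13.1 follows patients for toxicity and survival, and Section 9.1 sets survival contact every 3 months for at least 2 years. Deaths will therefore be captured more reliably than late progressions.

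**Working it through.** **1. Planned figures.** The documents give none for either duration. The only design figures concern the response rate, and they reproduce. With 2 or fewer responses of 16 stopping the trial and at least 9 of 31 required at the end, the exact early-stopping probability at a 16% response rate is 0.516 (stated as 52%). The type I error is 0.047 (limit 0.05) and the power at 35% is 0.801 (stated as 0.8). None of this depends on the duration definitions.

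**2. The definitions side by side.**

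| Endpoint | Start | Ends at progression | Ends at death | Censoring rule |
|---|---|---|---|---|
| PFS (14.0) | start of treatment | yes | yes | last tumour assessment |
| Duration of response (12.0, 14.0) | first response | yes | not named | none given |
| Stable disease (12.0) | start of treatment | yes | not named | none given |
| Stable disease (14.0) | not restated | not restated; limited to time on treatment | not named | none given |

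**3. Size of the effect.** Assume constant hazards: h_p for documented progression and h_d for death without it.

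- Death counted: median = ln 2/(h_p + h_d).
- Death censored: median = ln 2/h_p.
- Ratio = (h_p + h_d)/h_p = 1/(1-f), where f = h_d/(h_p + h_d) is the share of endings that are deaths without documented progression.

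The documents do not give f. Over an assumed range:

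| f | 0% | 5% | 10% | 20% | 25% | 30% | 40% |
|---|---|---|---|---|---|---|---|
| Median multiplied by | 1.00 | 1.05 | 1.11 | 1.25 | 1.33 | 1.43 | 1.67 |

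Worked example with assumed monthly hazards h_p = 0.15 and h_d = 0.02 to 0.05. With death censored the median is 0.693/0.15 = 4.62 months. With death counted it is 0.693/0.17 = 4.08 months (f = 0.02/0.17 = 12%) or 0.693/0.20 = 3.47 months (f = 0.05/0.20 = 25%). The ratios are 1.13 and 1.33.

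**4. Check by simulation.** The assumptions are exponential durations, a true median of 4 months with death counted, and 2,000 patients per run. Deaths are censored either at death or at the last six-weekly scan.

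| f | Death counted | Censored at death | Censored at last scan |
|---|---|---|---|
| 10% | 4.00 | 4.46 | 4.38 |
| 20% | 4.03 | 5.03 | 4.89 |
| 30% | 4.00 | 5.66 | 5.47 |

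The formula gives 4/0.9 = 4.44, 4/0.8 = 5.00 and 4/0.7 = 5.71. With only 11 patients per run the typical medians are similar (4.50, 5.04 and 5.69 when censored at death).

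**5. What f could be here.** Expected responders among 31 are 31 x 0.16 = 4.96 under the null and 31 x 0.35 = 10.85 under the alternative. One or two such deaths would be about 9-18% of 11 responders, or 20-40% of 5. No such deaths gives f = 0 and no bias.

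**The case against.** **The plan never says that deaths are censored.** That is correct; it is an inference. But it is what the stated end points produce under Kaplan-Meier when no other rule is given. Section 14.0 does say "Patients are considered non-responses (PD) if they are not evaluable (including if CT scan evaluation not available) or died during the study", which shows death treated as unfavourable. That sentence classifies patients for the response rate and supplies no end date for a duration. Deaths before the first reassessment, which Section 12.0 calls early deaths, should enter neither analysis, so the point concerns later deaths only.

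**A reader might infer that both durations are certainly overstated.** The documents do not support that for stable disease. If Section 14.0 governs, deaths after treatment stops may fall outside the window, and stopping for toxicity could end or censor the duration. The net direction is then not established.

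**A reader might take the 13-33% in the worked example as a finding.** It follows from assumed hazards. Scans about every six weeks, and the request in Section 12.0 to document progression even after discontinuation, both keep f down. It could be zero.

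**Counting death can also lengthen a duration.** A patient who stops with stable disease, has no further scans and dies many months later would have an event dated at death. This objection stands, and it is why adding death to the definition is not enough without a rule for late deaths.

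**The endpoints are secondary and descriptive.** This also stands: no test or decision rule uses them.

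**Conclusion.** The point holds for duration of response. Its stated end point omits death, the analysis method then censors deaths without documented progression, and the bias is upward whenever at least one such death occurs. It holds for duration of stable disease on the Section 12.0 definition. On the Section 14.0 wording the direction is uncertain, and the two sections conflict in any case.

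The size cannot be derived from the documents. Under constant hazards it is a factor of 1/(1-f) on the median: none at f = 0, 11% at f = 10%, 25% at f = 20% and 33% at f = 25%, with f assumed throughout. The response rate, the Simon boundaries, PFS, overall survival and the sample size do not change. This should be corrected before analysis, but it does not threaten the trial's main conclusion.

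**What to change.** In Sections 12.0 and 14.0:

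1. Define both durations as ending at the first of documented progression or death from any cause.
2. Otherwise censor at the last tumour assessment, as for PFS.
3. State how deaths after missed scans, or after new anticancer therapy, are handled. One option is to censor at the last tumour assessment before the gap or the new therapy. The PFS text does not spell these cases out, so the rule should be written down and be the same for PFS and both durations.
4. Reconcile the sections on whether duration of stable disease is limited to time on treatment. The documents do not show which was intended, so the sponsor must decide. If the limit stays, say whether stopping treatment without progression is an event or a censoring.

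The cost is a few sentences. Death dates are already collected for overall survival, so no new data are needed. Reported durations may be shorter.
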